Appendix 9. Provisions for Changes in Study Conduct During Exceptional Circumstances

There may be times of exceptional circumstances, such as pandemics or natural disasters, which may cause disruptions to the conduct of the study. Possible disruptions are limitations in the ability to conduct study procedures or ability to have on-site visits occur by participants.

To mitigate the risk of participants missing visits, to allow participants to safely continue in the study, and to maintain the data integrity of the study in the case of an exceptional circumstance, **sites may implement changes to the conduct of the study on a case-by-case basis following sponsor's written approval (if permitted by local regulations)**. Good Clinical Practice compliance and minimization of risks to study integrity are important considerations. Ensuring the safety of study participants is the prevailing consideration.

Additional written guidance will be provided by the sponsor in the event written approval is granted for changes in study conduct.

The following changes in study conduct captured in this appendix will not be considered protocol deviations. Missing data will be captured as protocol deviation(s).

1. Remote visit (telephone/telemedicine)

Telephone or technology-assisted virtual visits (telemedicine) to complete appropriate assessments are acceptable if in-person site visits are not possible. The study site should capture the visit location and method with a specific explanation for any data missing because of missed in-person site visits in source document and eCRF. The site must discuss with the patient and ensure consent to the proposed remote operational plan. This communication should be documented in the patient's records.

Examples of assessments that may be completed via telephone/telemedicine visit include the following:

- AEs and product complaints
- concomitant medications
- review of study participant diary (including study drug compliance)

2. Remote Assessment and Data Collection

Patient visit and data collection can be done remotely for treatment period A and treatment period B. The PI/Sub-I is to document all teleconferences/remote visits in the patient's records. Site facing assessments can be completed on paper (preferably eCOA if the site is able) and patient facing assessments will be conducted in interview format with the qualified personnel documenting the patient's responses on paper. Sponsor will provide guidance for performing these assessments (CHQ-PF50, EQ-5D). For ophthalmology assessments, PI should direct patient care based on symptom-directed physical examination. Ophthalmology assessments are required to be completed every 8 weeks.

3. Investigational product and ancillary supplies

In cases when a patient is unable to come to site to receive trial supplies during a normal on-site visit, the site should work with the sponsor to determine appropriate actions to receive trial supplies. This may include a participant coming to the site to receive trial supplies only from site staff without full completion of a visit, a participant-approved designee coming to the site to receive trial supplies on a participant's behalf, or delivery to a participant's home.

The following requirements must be met:

- sponsor approves the alternative method of delivery, taking local regulatory requirements into consideration
- participant consents to alternate method of delivery as defined by local regulations
- site confirms the participant's receipt of the trial supplies
- site/sponsor confirms appropriate ethics review board notification
- alternate delivery of IP should be performed in a manner that does not compromise treatment blinding and ensures product integrity. The existing protocol requirements for product accountability remain unchanged.
- when delivering supplies to a patient's home:
 - participant consent must include provision of any personal information
 - site should ensure oversight of the shipping process to ensure accountability and product quality (i.e., storage conditions and intact packaging upon receipt)
- additional instructions should be provided to the participant on how to return any unused or completed trial supplies.

4. Local laboratory option

In exceptional circumstances, to ensure patient safety and with the sponsor's prior written approval, local laboratory testing may be conducted in lieu of central laboratory testing. The local laboratory must be qualified in accordance with local regulations. Clinically significant laboratory findings must be recorded as an adverse event in the AE eCRF.

For patients unable to access investigator sites, laboratory testing will be obtained and collected at least every 8 weeks in treatment period A and every 12 weeks in treatment period B. The first collection should be 8 weeks or 12 weeks, respectively, from the patient's last collected central laboratory samples.

When collecting local labs, sites should store records from the labs including results, address, certification (College of American Pathologists/Clinical Laboratory Improvement Amendments, [CAP/CLIA]) status, and reference ranges. The PI/Sub-I should sign and date review of local labs per normal process and follow-up with the patient as needed. Local labs may be sent to the patient as this is standard process in clinical care.

The laboratory measures listed below are the **minimum** required in order to monitor patient safety and determine temporary or permanent discontinuation of IP. Additionally, investigators should include any symptom-based laboratory testing based on their interactions with their patients. As stated in the protocol, investigators are responsible for monitoring the overall health of their patients.

The investigators should request the following laboratory analyses:

- WBC
- ANC
- Lymphocyte count
- Platelet count
- Hemoglobin
- ALT, AST, total bilirubin, INR
- ESR
- Urine pregnancy

These laboratory results will allow the investigators to follow both the temporary and permanent discontinuation criteria as provided in the protocol (Section 8.1.1, Temporary Interruption of Investigational Product and Section 8.1.2, Permanent Discontinuation from Investigational Product).

5. Documentation

a. Changes to study conduct

Changes to study conduct will be documented as the following:

- Sites will need to identify and document the details of how all participants, visits, methods, and activities conducted were affected by exceptional circumstances. All dispensing/shipment records of IP and relevant communications, including delegation, should be filed with site trial records.
- The site should document the participant's consent for having remote visits and remote dispensing of IP, ancillaries, and diaries, prior to implementation of these activities.
- Source document(s) that are generated at participant's home should be part of the investigator's source documentation and should be transferred to the site in a secure and timely manner.

b. Missing data and other protocol deviations

The study site should capture specific explanations for any missing data and other protocol deviations in source documents and eCRF. While protocol deviations may be unavoidable in an

exceptional circumstance, documentation of deviations and missing data will be important for data analysis and reporting.

Details of changes in analyses to specifically accommodate exceptional circumstances will be further described in the study SAP.

6. Informing ethical review boards (ERBs)

The sponsor and study investigators will notify ERBs as soon as possible to communicate implementation of changes in study conduct due to exceptional circumstances. To protect the safety of study participants, urgent changes may be implemented before such communications are made, but all changes will be reported as soon as possible following implementation.

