- h Applicable for sites in Germany only.
- k Performed locally. To be drawn prior to dosing early in the visit.
- l For patients who are positive for HBcAb, a follow-up test for HBV DNA is required. Patients with a positive HBcAb will return to the site and have an HBV DNA sample drawn, which will be processed centrally. Results must be known prior to enrollment. Any enrolled patient who is HBcAb positive, regardless of HBsAb status or level, must undergo HBV DNA testing per the schedule of activities.
- m Urine pregnancy tests are required for females ≥ 10 years of age (<10 years at investigator discretion) if menarche reached or if there is reason to believe the patient is sexually active.
- n Clinical chemistry will include eGFR (calculated by Bedside Schwartz 2009 formula).
- o Fasting lipid profile: Patients should not eat or drink anything except water for 4-12 hours depending on weight and age as specified below. If a patient attends these visits in a nonfasting state, this will not be considered a protocol violation. Recommended fasting times by age and weight are as follows:
 - Patients ≥ 12 years: fast for 12 hours prior to laboratory test
 - Patients 8 to <12 years and weighing >50 kg: fast for 12 hours prior to laboratory test
 - Patients 8 to <12 years and weighing ≤ 50 kg: fast for 8 hours prior to laboratory test
 - Children <8 years and weighing 25 to ≤ 50 kg: fast for 8 hours prior to laboratory test
 - Children <8 years and weighing 10 to <25 kg: fast for 6 hours prior to laboratory test
 - Children <8 years and weighing <10 kg: fast for 4 hours prior to laboratory test

^p If patients are eligible for vaccination with tetanus, diphtheria, and pertussis (TDaP) and/or pneumococcal conjugate vaccine according to local recommended schedule of vaccination, IgG titers for eligible vaccine will be evaluated at prevaccination, 4 weeks postvaccination, and 12 weeks postvaccination.

^q Estradiol (for females) or testosterone (for males) will be collected for the assessment of pubertal development in patients aged 8 to <18 years.

^r Participants 8 years and older will be assessing their sexual maturity. Once the participant reaches the score 5 in the scale, no further assessments are needed.

Note: Due to blood volume restrictions, some laboratory tests may not be collected. Laboratory samples are recommended to be collected as described in the sponsor-provided weight-based prioritization chart ([Appendix 7](#)).

3. Introduction

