8.1. Discontinuation from Study Treatment

8.1.1. *Temporary Interruption of Investigational Product*

In some circumstances, patients may need to temporarily interrupt treatment as a result of AEs or abnormal laboratory values that may have an unclear relationship to investigational product.

Except in cases of emergency, it is recommended that the investigator consult with Lilly (or its designee) before temporarily interrupting therapy for reasons other than those defined in [Table JAHW.8](#).

For the abnormal laboratory findings and clinical events (regardless of relatedness) listed in [Table JAHW.8](#), specific guidance is provided for temporarily interrupting treatment and when treatment may be restarted. Retest frequency and timing of follow-up laboratory tests to monitor the abnormal finding is at the discretion of the investigator. Investigational product that was temporarily interrupted because of an AE or abnormal laboratory value not specifically covered in [Table JAHW.8](#) may be restarted at the discretion of the investigator.

Table JAHW.8. Criteria for Temporary Interruption of Investigational Product

Hold Investigational Product if the Following Laboratory Test Results or Clinical Events Occur:	Investigational Product May be Resumed When:
WBC count <2000 cells/ μ L (<2.00 x 10 ³ / μ L or <2.00 billion/L)	WBC count \geq 3000 cells/ μ L (\geq 3.00 x 10 ³ / μ L or \geq 3.00 billion/L)
ANC <1000 cells/ μ L (<1.00 x 10 ³ / μ L or <1.00 billion/L)	ANC \geq 1500 cells/ μ L (\geq 1.50 x 10 ³ / μ L or \geq 1.50 billion/L)
Lymphocyte count <500 cells/ μ L (<0.50 x 10 ³ / μ L or <0.50 billion/L)	Lymphocyte count \geq 1000 cells/ μ L (\geq 1.00 x 10 ³ / μ L or \geq 1.00 billion/L)
Platelet count <75,000/ μ L (<75 x 10 ³ / μ L or <75 billion/L)	Platelet count \geq 100,000/ μ L (\geq 100 x 10 ³ / μ L or \geq 100 billion/L)
eGFR <40 mL/min/1.73 m ² (from serum creatinine) for patients with screening eGFR \geq 60 mL/min/1.73 m ²	eGFR \geq 50 mL/min/1.73 m ²
eGFR <30 mL/min/1.73 m ² (from serum creatinine) for patients with screening eGFR \geq 40 to <60 mL/min/1.73 m ²	eGFR \geq 40 mL/min/1.73 m ²
ALT or AST >5 x ULN	ALT and AST return to <2 x ULN, and IP is not considered to be the cause of enzyme elevation
Hemoglobin <8 g/dL (<80.0 g/L)	Hemoglobin \geq 10 g/dL (\geq 100.0 g/L)
Symptomatic herpes zoster	All skin lesions have crusted and are resolving

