8.1.2. Permanent Discontinuation from Investigational Product

Investigational product must be permanently discontinued if the patient or the patient's designee requests to discontinue investigational product.

Discontinuation of the investigational product for abnormal liver tests should be considered by the investigator after consultation with the Lilly-designated medical monitor when a patient meets 1 of the following conditions:

- ALT or AST $>8 \times$ ULN
- ALT or AST $>5 \times$ ULN for more than 2 weeks after temporary interruption of investigational product
- ALT or AST $>3 \times$ ULN and TBL $>2 \times$ ULN or international normalized ratio (INR) >1.5
- ALT or AST $>3 \times$ ULN with the appearance of fatigue, nausea, vomiting, right upper-quadrant pain or tenderness, fever, rash, and/or eosinophilia ($>5\%$)
- ALP $>3 \times$ ULN that is deemed to be of liver origin and drug-related
- ALP $>2.5 \times$ ULN and TBL $>2 \times$ ULN
- ALP $>2.5 \times$ ULN with the appearance of fatigue, nausea, vomiting, right upper-quadrant pain or tenderness, fever, rash, and/or eosinophilia ($>5\%$)

Note: Patients who are discontinued from investigational product due to a hepatic event or liver test abnormality should have additional hepatic safety data collected via the hepatic safety eCRF.

Investigational product should be permanently discontinued if any of the following laboratory abnormalities are observed:

- White blood cell count $<1000 \text{ cells}/\mu\text{L}$ ($1.00 \times 10^3/\mu\text{L}$ or $1.00 \text{ billion}/\text{L}$)
- ANC $<500 \text{ cells}/\mu\text{L}$ ($0.50 \times 10^3/\mu\text{L}$ or $0.50 \text{ billion}/\text{L}$)
- Lymphocyte count $<200 \text{ cells}/\mu\text{L}$ ($0.20 \times 10^3/\mu\text{L}$ or $0.20 \text{ billion}/\text{L}$)
- Hemoglobin $<6.5 \text{ g/dL}$ ($<65.0 \text{ g/L}$)

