9.4.5. Hepatic Safety Monitoring and Data Collection

If a study patient experiences elevated ALT ≥ 3 x ULN, ALP ≥ 2 x ULN, or elevated TBL ≥ 2 x ULN, liver testing (Appendix 4) should be repeated within 3 to 5 days including ALT, AST, ALP, TBL, direct bilirubin, gamma-glutamyl transferase, and creatine phosphokinase to confirm the abnormality and to determine if it is increasing or decreasing. If the abnormality persists or worsens, clinical and laboratory monitoring should be initiated by the investigator and in consultation with the study medical monitor. Monitoring of ALT, AST, TBL, and ALP should continue until levels normalize or return to approximate baseline levels. Discontinuation criteria of investigational products, either temporary interruption or permanent discontinuation, due to abnormal ALT, AST, TBL, or ALP, are detailed in Section 8.1.

Additional safety data should be collected via the hepatic eCRF if 1 or more of the following conditions occur:

- ALT ≥ 5 x ULN confirmed by repeat testing
- ALP ≥ 2 x ULN confirmed by repeat testing
- TBL ≥ 2 x ULN confirmed by repeat testing (except for cases of known Gilbert’s syndrome)
- Permanent discontinuation of investigational product due to hepatic event or hepatic laboratory abnormality
- Hepatic SAE

Refer to [Appendix 4](#) for a description of hepatic laboratory values that warrant exclusion from the study, temporary or permanent discontinuation of investigational product (Section 8.1), or additional safety collection via the hepatic eCRF.

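### The Appendix 9 minimum local laboratory list is said to be enough to apply the interruption and discontinuation criteria, but it omits creatinine/eGFR and ALP (and eosinophils), so some criteria cannot be applied from it

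*Protocol*

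**What the plan says.** Appendix 9 covers exceptional circumstances such as pandemics. Item 4 permits local in place of central testing, with the sponsor's prior written approval. Patients who cannot reach a site are sampled at least every 8 weeks in Part A and every 12 weeks in Part B.

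The stated minimum is WBC, ANC, lymphocytes, platelets, hemoglobin, "ALT, AST, total bilirubin, INR", ESR and urine pregnancy. Beyond this, "investigators should include any symptom-based laboratory testing based on their interactions with their patients". The item then concludes: "These laboratory results will allow the investigators to follow both the temporary and permanent discontinuation criteria as provided in the protocol", citing Sections 8.1.1 and 8.1.2.

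Those sections use analytes that are not on the list:

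- **Table JAHW.8 (Section 8.1.1)** has two hold rows based on eGFR, each worded "from serum creatinine) for patients with screening eGFR" and then a screening range.
- **Section 8.1.2** lists ALP above 3 × "ULN that is deemed to be of liver origin and drug-related" as a condition for considering discontinuation. Two further conditions use ALP above 2.5 × ULN.
- **Section 8.1.2** also has two liver conditions whose qualifying features end in "right upper-quadrant pain or tenderness, fever, rash, and/or eosinophilia" above 5%.

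**The concern.** The sentence in Appendix 9 does more than set a floor. It tells the site that the floor is enough to apply the stopping rules, so a site that reads it has no reason to order anything else for a child who seems well.

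The eGFR rows and the isolated ALP condition are laboratory thresholds that apply without symptoms. If the analyte is never measured, the rule cannot operate, and neither can the eGFR values that Table JAHW.8 sets for restarting drug.

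Renal function matters to dosing in this protocol. The eGFR exclusion limit is 40 mL/min/1.73 m², so children with eGFR from 40 to below 60 can enroll. Under Section 7.1 they receive half the baricitinib dose, and one of the two eGFR hold rows is written for exactly that group. In routine conduct, clinical chemistry including eGFR is scheduled at every treatment visit in both parts. Appendix 9 drops it when in-person oversight is weakest.

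**Working it through.** No formula applies. The check compares each laboratory criterion in Sections 8.1.1 and 8.1.2 with the 11 items on the Appendix 9 list.

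**Section 8.1.1, Table JAHW.8.** There are 10 rows: 8 laboratory and 2 clinical (herpes zoster, other infection).

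| Hold criterion | On the list? |
|---|---|
| WBC <2000 cells/µL | Yes |
| ANC <1000 cells/µL | Yes |
| Lymphocytes <500 cells/µL | Yes |
| Platelets <75,000/µL | Yes |
| eGFR <40 (screening eGFR ≥60) | **No** |
| eGFR <30 (screening eGFR ≥40 to <60) | **No** |
| ALT or AST >5 × ULN | Yes |
| Hemoglobin <8 g/dL | Yes |

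Result: 6 of 8 covered, 2 of 8 not covered.

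**Section 8.1.2, liver conditions.** There are 7, of which 3 use ALP.

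| Condition | Can it be applied from the list? |
|---|---|
| ALT/AST >8 × ULN | Yes |
| ALT/AST >5 × ULN for more than 2 weeks after interruption | Yes |
| ALT/AST >3 × ULN with TBL >2 × ULN or INR >1.5 | Yes |
| ALT/AST >3 × ULN with symptoms or eosinophilia | Yes, except the eosinophilia element |
| ALP >3 × ULN, hepatic and drug-related | **No; nothing listed prompts an ALP test** |
| ALP >2.5 × ULN with TBL >2 × ULN | Indirectly, through TBL |
| ALP >2.5 × ULN with symptoms or eosinophilia | Largely, through symptom-based testing; not the eosinophilia element |

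The sixth condition is reached through Section 9.4.5. When ALT is at least 3 × ULN, or ALP or TBL is at least 2 × ULN, liver testing "should be repeated within 3 to 5 days including ALT, AST, ALP, TBL, direct bilirubin". TBL is on the list, so a raised TBL brings in ALP. An isolated ALP rise has no such entry point, because ALP is its only trigger and ALP is not measured.

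Result: 1 of 7 has no trigger, and 2 of 7 have an eosinophilia element that the list does not measure.

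**Section 8.1.2, hematology thresholds.** WBC, ANC, lymphocytes and hemoglobin: 4 of 4 covered.

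**Other laboratory-based stops in Section 8.1.2.** Pregnancy is covered by the urine test. HBV DNA is not listed, but footnote l to Table JAHW.2 says that enrolled HBcAb-positive patients "must undergo HBV DNA testing per the schedule of activities". The obligation therefore stands, and the silence in Appendix 9 calls for clarification; it is not a gap in the rules.

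**The case against.** The strongest case on the other side is that this is one sentence in a contingency appendix.

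- **Safeguards around the appendix.** Changes are case by case with the sponsor's written approval, and further written guidance is promised. The list is labelled a minimum, and symptom-based testing is added. All of this is true, and the guidance is not among the documents. But no text requires that guidance to add creatinine or ALP, and neither an eGFR threshold nor an isolated ALP threshold depends on symptoms.
- **The 2 of 8 count.** The two eGFR rows are mutually exclusive by screening eGFR. For any one patient, 8 − 1 = 7 laboratory rows apply and 1 is uncovered. This is a fair way to see it: the omission is one analyte, and the rule is a temporary hold, since eGFR is not a permanent-discontinuation criterion.
- **ALP.** The liver conditions call for consideration after consulting the medical monitor, so they are not automatic stops. The isolated ALP condition also needs a judgment on liver origin and drug cause. That limits its weight, but the judgment cannot begin without an ALP value.
- **Eosinophils.** This is the weakest element. Eosinophilia is one and/or item among symptoms, the Appendix 4 hepatic panel includes eosinophils, and a local differential run for ANC may report them. The list still does not ask for them.
- **Size of the risk.** The documents give no rate for these events, and entry excludes eGFR below 40 and ALP at or above 2 × ULN. The number of children affected cannot be estimated.

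**Conclusion.** The point holds. The sufficiency statement in Appendix 9 contradicts Sections 8.1.1 and 8.1.2. From the listed tests, 2 of 8 laboratory hold rows (both eGFR) cannot be applied, 1 of 7 liver conditions (isolated ALP above 3 × ULN) has no trigger, and 2 of 7 have an unmeasured eosinophilia element. Creatinine/eGFR is the main omission, ALP comes second and eosinophils are minor.

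This is a safety-monitoring inconsistency confined to exceptional-circumstances local testing. It does not touch the primary endpoint, the Bayesian decision rules or the sample size. The conclusion assumes that a site follows the list as written, that the child has no symptoms that would prompt other tests, and that unseen sponsor guidance does not add the missing analytes.

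**What to change.** Amend Appendix 9 item 4:

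1. Add serum creatinine with eGFR, ALP, and a WBC differential including eosinophils to the minimum list.
2. Add one line that HBcAb-positive patients continue scheduled HBV DNA testing, arranged locally or centrally.

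The sufficiency sentence can then stay, because it becomes true. No criterion or threshold changes.

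The cost is a short appendix amendment and a few more analytes. Creatinine and ALP can come from the chemistry sample already needed for ALT, AST and bilirubin, and eosinophils from the blood count already needed for ANC and lymphocytes. The Appendix 7 weight-based chart excludes no chemistry or hematology panel at any weight, so blood volume in small children is no obstacle. HBV DNA needs its own arrangement, but only for HBcAb-positive patients, and the schedule already requires it.
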